4.2 Secondary Endpoints

The secondary endpoints are DOR, CR rate, duration of CR, PFS and OS. All these endpoints are based on Lugano classification 2014 and Global Response score for the CTCL subjects.

DOR will be calculated from the date of initial documentation of a response (CR, or PR) to the date of first documented evidence of progressive disease (or relapse for subjects who experience CR during the study) or death due to any cause, whichever occurs first. Subjects who are progression-free and alive or have unknown status will be censored at the last tumor assessment. For subjects who received subsequent therapy prior to documented progression, duration of response will be censored on the last tumor assessment date prior to or on subsequent therapy. Allogeneic SCT and ASCT will be considered as subsequent therapy.

The CR rate is defined as the number of subjects with a BOR of CR divided by the number of treated subjects. The duration of CR will only be evaluated in subjects with BOR of CR and is defined as the time from first documentation of CR to the date of relapse or death due to any cause, whichever occurs first. Censoring will be applied as per DOR definition.

PFS is defined as the time from the date of first dose of study drug until the date of first documented evidence of progressive disease (or relapse for subjects who experience CR during the study) or death due to any cause, whichever comes first. Subjects who are progression-free and alive or have unknown status will be censored at the last tumor assessment. Subjects who did not have any on-study tumor assessments and did not die will be censored on the date of first treatment. For subjects who received subsequent therapy prior to documented progression, it will be censored on the last tumor assessment date prior to or on subsequent therapy.

Situation	Date of Progression or Censoring	Outcome
No baseline tumor assessments	First dose date	Censored
No on study tumor assessments and no death	First dose date	Censored
New anticancer treatment started without a prior reported progression or death	Date of last evaluable tumor assessment prior to or on the date of initiation of the subsequent anti-cancer therapy	Censored
Progression documented at scheduled or unscheduled visit and no new anticancer treatment started before	Date of the first documented tumor progression	Progressed
Subject progression free and no new anticancer treatment started	Date of last tumor assessment	Censored
Death without prior progression and no new anticancer treatment started	Date of death	Progressed

Table 4.2-1:Censoring Scheme for PFS

OS is defined as the time from the date of first dose of study drug until the date of death (any reason). If the subject is alive or the vital status is unknown, the subject will be censored at the date the subject was last known to be alive.

5 SAMPLE SIZE AND POWER

5.1 Sample Size Determination

- In the Dose Evaluation Phase (Cohort A), 6-12 subjects will be treated. The number of subjects is not based on statistical power considerations. If one or less (<=1) of 6 subjects experience a DLT, the upper limit of the 80% 1-sided exact confidence interval for the true DLT rate will not be greater than 42%. If 3 or less (≤ 3) of 12 subjects experience a DLT, the upper limit of the 1-sided 80% exact confidence interval (CI) for the true DLT rate will not be greater than 41.2%.
- In the Expansion Phase (Cohort B), A total of 130 subjects will be treated, with 40 subjects in cohort B1 (DLBCL), 30 subjects in cohort B2 (PTCL) and 20 subjects in B3 (CTCL), 30 subjects in cohort B4 (PMBL) and 10 subjects in cohort B5 (MGZL).
 - Given 40 subjects in DLBCL, the two-sided 80% confidence interval for the ORR is 48.6%
 70.6% if we assume an observed ORR rate of 60%. The lower bound of CI excludes 40%, which is the null hypothesis ORR rate for PTCL.
 - Given 30 subjects in PTCL, the two-sided 80% confidence interval for the ORR is 46.7%
 72.3% if we assume an observed ORR rate of 60%. The lower bound of the CI excludes 40%, which is the null hypothesis ORR rate for PTCL.
 - Given 20 subjects in CTCL, the two-sided 80% confidence interval for ORR is 63.9% -91.0% if we assume an observed ORR rate of 80%. The lower bound of the CI excludes 60%, which is the null hypothesis ORR rate for CTCL.
 - Given 30 subjects in PMBL, the two-sided 80% confidence interval for the ORR is 37.0%
 63.0% if we assume an observed ORR rate of 50%. The lower bound of the CI excludes 30%, which is the null hypothesis ORR rate for PMBL.
 - Given 10 subjects in MGZL, the two-sided 80% confidence interval for the ORR is 11.6%
 55.2% if we assume an observed ORR rate of 30%. The lower bound of the CI excludes 10%, which is the null hypothesis ORR rate for MGZL.

Table 5.1-1 summarizes the 80% exact CI for different targeted ORRs and sample sizes.

Table 5.1-1:Two-sided 80% Exact CI for different n of subjects in each cohort	
	If the observed ORR rate is 60% in Cohort B1 and B2
N=30	[46.7% - 72.3%]
N=40	[48.6% - 70.6%]
	If the observed ORR rate is 80% in Cohort B3
N=20	[63.9% - 91.0%]
	If the observed ORR rate is 50% in Cohort B4
N=30	[37.0% - 63.0%]
	If the observed ORR rate is 30% in Cohort B5
N=10	[11.6% - 55.2%]

If the screening failure rate is 20%, we would need to enroll 170 subjects to have 136 patients treated (130 in Cohort B, 6 in Cohort A). If Cohort A needs 6-12 more treated subjects, we would need to enroll 8-15 more subjects accordingly.

6 STUDY PERIODS, TREATMENT REGIMENS AND POPULATIONS FOR ANALYSES

6.1 Study Periods

See Core Safety SAP.

6.2 Treatment Regimens

Subjects will receive brentuximab vedotin (BV) 1.8mg/kg and nivolumab 240mg flat dose or BV 1.2mg/kg and nivolumab 240mg flat dose.

6.3 **Populations for Analyses**

- All Enrolled Subjects: All subjects who signed an informed consent form and were registered into the IVRS.
- All Treated Subjects: All subjects who received at least one dose of any of the study drugs. This is the primary population for safety and efficacy analyses. This dataset will be used for baseline demographics and efficacy and safety analyses.
- **Response Evaluable Subjects**: Treated subjects whose tumor measurements (PET CT or CT/MRI) were made at baseline and at least one on-study tumor assessment.

7 STATISTICAL ANALYSES

7.1 General Methods

All analyses will be performed on the all treated subjects and will be conducted separately for the NHL subtype groups (DLBCL, CTCL, PTCL, PMBL, MGZL).

As there was only one dose explored in the dose evaluation cohort A (brentuximab vedotin 1.8mg/kg and nivolumab 240mg) subjects from cohort A (dose evaluation) and cohort B (dose expansion) will be combined for all analyses, unless otherwise noted. A couple of safety analysis will be conducted on the cohort A subjects only to support the dose evaluation process (see Section 7.6.1).

The bulleted titles in the following subsections describe tabulations of discrete variables, by the frequency and proportion of subjects falling into each category, grouped by cohort. Percentages given in these tables will be rounded and, therefore, may not always sum to 100%. Continuous variables will be summarized by cohort using the mean, standard deviation, median, minimum and maximum values.

Time to event distribution (i.e. progression free survival, overall survival and duration of response) will be estimated using Kaplan Meier techniques.

Median survival time along with 95% CI will be constructed based on a log-log transformed CI for the survivor function $S(t)^{4,5}$. Rates at fixed timepoints will be derived from the Kaplan Meier estimate and corresponding confidence interval will be derived based on Greenwood formula⁶ for variance derivation and on log-log transformation applied on the survivor function $S(t)^7$.

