follow-up visits may be done in person or by phone. All treated subjects will be followed for survival at least every 3 months until death or lost to follow-up. Subjects with residual toxicity G \geq 2 at the time of discontinuation must follow these until resolved to at least G1, end of study or deemed irreversible, whichever occurs first. Subjects who discontinue for reasons different than progressive disease must continue to perform tumor assessments as described in [Section 5.4](#) until disease progression is documented.

The primary endpoint for Cohort B will be investigator-assessed ORR for all five tumor types. Primary endpoint analysis will occur 8 months after the last patient receives their first treatment (LPFT). Depending on the enrollment for each disease cohort, the analysis may be done at different times for each cohort, or at the same time for the five cohorts. The study design schematic is presented in [Figure 3.1-1](#).

Figure 3.1-1: Study Design Schematic

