Table 8.1-1 summarizes the 90% exact CI for different targeted ORRs and sample sizes. The targeted ORR of 60% in DLBCL and PTCL and 80% in CTCL, and null hypothesis ORR rate of 40% in DLBCL and PTCL and 60% in CTCL are based on the historical data and the activity of brentuximab vedotin and nivolumab as single agents from phase I and phase II studies.
[19,39,86,87](#)

Table 8.1-1: One-sided 90% Exact CI for different number of subjects in each cohort		
	If the observed ORR rate is 60% in Cohort B1 and B2	Power
N=30	[46.7% - 72.3%]	82%
N=40	[48.6% - 70.6%]	87%
If the observed ORR rate is 80% in Cohort B3		
N=20	[63.9% - 91.0%]	62 %
If the observed ORR rate is 50% in Cohort B4		
N=30	[37.0% - 63.0%]	81 %
If the observed ORR rate is 30% in Cohort B5		
N=10	[11.6% - 55.2%]	61%

Also, If we have 20 subjects in Cohort B3, assuming true ORR is 80%, there will be approximately 62% power to reject null hypothesis that the true ORR is $\leq 60\%$, considering a one-sided alpha of 10%. Given a very low prevalence of CTCL, 20 subjects in cohort III is considered as feasible and adequate for a phase II signal detecting trial. Sample size of 30 subjects in Cohort B2 and 40 subjects in Cohort B1 are corresponding to power of 82% and 87% respectively to reject null hypothesis that the true ORR is $\leq 40\%$ assuming true ORR is 60% and considering a one-sided alpha of 10%. If we have 30 subjects in Cohort B4, assuming true ORR is 50%, there will be approximately 81% power to reject null hypothesis that the true ORR is $\leq 30\%$, considering a one-sided alpha of 10%. Finally if we have 10 subjects in Cohort B5, assuming true ORR is 30%, there will be approximately 61% power to reject null hypothesis that the true ORR is $\leq 10\%$, considering a one-sided alpha of 10%.

If the screening failure rate is 20%, we would need to enroll 170 subjects to have 136 patients treated (130 in Cohort B, 6 in Cohort A). If Cohort A needs 6-12 more treated subjects, we would need to enroll 8-15 more subjects accordingly.

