8.4.2 Efficacy Analyses

All analyses will be performed separately for each cohort and also for all treated subjects combined with same treatment dosage (ie, safety cohort subjects with different dose from the expansion cohort will not be combined).

The ORR will be summarized by binomial response rates and their corresponding two-sided 80% exact CIs using the Clopper-Pearson method. The same analysis will be performed for CR rate.

The DOR will be summarized by cohort for subjects who achieve confirmed PR or CR using the Kaplan-Meier (KM) product-limit method. Median values of DOR, along with two-sided 95% CI using log-log transformation method and range, will also be calculated. The same analysis will be performed for duration of CR, PFS and OS at 1 year. Detailed analyses on efficacy endpoints will be presented in the statistical analyses plan.

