7.5 Efficacy Analyses

7.5.1 Primary Efficacy Endpoint

The primary endpoint ORR will be summarized for all treated subjects by binomial response rate and its corresponding two-sided 80% exact CIs using the Clopper-Pearson method.

BOR categories will be tabulated.

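### The SAP makes pooled Cohort A+B the only ORR analysis, although the protocol ties, sizes and powers the primary ORR endpoint on Cohort B alone

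*SAP*

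**What the plan says.** Protocol 3.1 states: "The primary endpoint for Cohort B will be investigator-assessed ORR for all five tumor types". The same section describes the 40/30/20/30/10 expansion subjects as additional to Cohort A. Protocol 8.1 gives every interval, null rate and power for those numbers, and says that Cohort A's 6 to 12 subjects were not chosen on power grounds.

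Protocol 8.4.2 then sets the analysis rule: "All analyses will be performed separately for each cohort and also for all treated subjects combined with same treatment dosage", with the rider that "safety cohort subjects with different dose from the expansion cohort will not be combined". Two analyses are therefore planned, one by cohort and one pooled at the same dose.

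SAP 7.1 gives its reason, "As there was only one dose explored in the dose evaluation cohort A", and concludes that "subjects from cohort A (dose evaluation) and cohort B (dose expansion) will be combined for all analyses, unless otherwise noted", by lymphoma subtype. The only exception it names is on the safety side: "A couple of safety analysis will be conducted on the cohort A subjects only to support the dose evaluation process" (the DLT outputs of SAP 7.6.1). SAP 7.5.1 reads: "The primary endpoint ORR will be summarized for all treated subjects by binomial response rate", with a two-sided 80% Clopper-Pearson interval. No Cohort B-only ORR appears. SAP 5.1 nevertheless repeats the Cohort B-only sizes, intervals and null rates; it omits the powers.

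**The concern.** The two documents disagree on the analysis set for the primary efficacy endpoint, and the SAP does not flag the departure, although SAP 7.5.2 does flag that time to response was not a protocol endpoint.

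Two things are at stake. First, the sizes, intervals, thresholds and powers describe an analysis that the SAP no longer specifies. Second, Protocol 3.1 says that all available Cohort A efficacy and safety data would be used to select the regimen for expansion. Pooling puts those same subjects into the primary estimate for that regimen. In an open-label study whose SAP (31 January 2017) speaks of Cohort A in the past tense, their responses could have been known when the analysis set was settled.

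**Working it through.** **Inputs.** Sizes, null and target ORRs and the one-sided 10% level are from Protocol 8.1; Cohort A's size of 6 to 12 is from Protocol 8.1 and SAP 5.1. The split of Cohort A by subtype is not given (Protocol 3.1 calls the first six subjects all comers), so m, the number added to a subtype, is an assumption.

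**Step 1: reproduce the plan.** For n subjects, r is the smallest count with P(X ≥ r | n, p0) ≤ 0.10, and power is P(X ≥ r | n, p1). This r is also the smallest count at which the lower limit of the two-sided 80% exact interval exceeds p0.

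| Cohort | n | p0 / p1 | r | Exact alpha | Power | Protocol 8.1 |
|---|---|---|---|---|---|---|
| B1 DLBCL | 40 | 40% / 60% | 21 | 7.4% | 87.0% | 87% |
| B2 PTCL | 30 | 40% / 60% | 16 | 9.7% | 82.5% | 82% |
| B3 CTCL | 20 | 60% / 80% | 16 | 5.1% | 63.0% | 62% |
| B4 PMBL | 30 | 30% / 50% | 13 | 8.4% | 81.9% | 81% |
| B5 MGZL | 10 | 10% / 30% | 3 | 7.0% | 61.7% | 61% |

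All five powers reproduce to within about one point, and so do all five intervals (the MGZL interval at 3/10 responders). The stated design is Cohort B only.

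**Step 2: pool m Cohort A subjects.** Replace n by N = n + m and recompute r.

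| Subtype | m | r/N | Alpha | Power |
|---|---|---|---|---|
| CTCL | 1 | 16/21 | 9.6% | 76.9% |
| CTCL | 6 | 20/26 | 5.6% | 74.7% |
| PTCL | 1 | 17/31 | 6.8% | 78.1% |
| PTCL | 2 | 17/32 | 9.2% | 83.5% |
| PTCL | 6 | 19/36 | 8.3% | 85.4% |
| DLBCL | 1 | 21/41 | 9.7% | 90.3% |
| DLBCL | 6 | 24/46 | 6.4% | 89.1% |

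Power can rise or, because counts are discrete, fall (PTCL, m = 1). Alpha stays at or below 10% by construction; for m = 1 to 6 the largest value in any subtype is 9.65% (DLBCL, m = 1).

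**Step 3: condition on known Cohort A results.** With a responders among m, conditional alpha is P(X_B ≥ r − a | n, p0), where r is the pooled threshold.

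- CTCL, m = 1: 5.1% at 0/1, 12.6% at 1/1.
- DLBCL, m = 1: 7.4% at 0/1, 13.0% at 1/1.
- PTCL, m = 2: 4.8% at 0/2, 9.7% at 1/2, 17.5% at 2/2.

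These average back to the pooled alpha. For PTCL, with null probabilities 0.36, 0.48 and 0.16: 0.36 × 4.81 + 0.48 × 9.71 + 0.16 × 17.54 = 9.2%.

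**Step 4: worst case if the set were chosen after seeing Cohort A.** Take the larger of the B-only alpha and the conditional alpha at each a, weighted by the null probability of a. For PTCL, m = 2: 0.36 × 9.71 + 0.48 × 9.71 + 0.16 × 17.54 = 11.0%. By the same sum, m = 6 gives 8.8%, 11.6%, 7.4%, 11.3% and 9.9% for B1 to B5, and no subtype exceeds 11.6% for m up to 6. Only if nearly all of a 12-subject Cohort A fell in one subtype does it reach 12.5% (PMBL, m = 12) or 13.2% (PTCL, m = 11).

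**The case against.** The best defence is that pooling is not new. Protocol 8.4.2 already allows it at the same dose, and the SAP's reason is that condition. Protocol 8.2 also calls all treated subjects the primary efficacy population, and both analysis sections specify estimation with an 80% interval rather than a formal test. This largely stands. What it does not cover is the loss of the separate analysis: Protocol 8.2 defines its populations within each cohort, 8.4.2 asks for both analyses, and SAP 5.1 still sets the intervals against null rates using Cohort B numbers.

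It can also be said that SAP 7.1 tabulates discrete variables by cohort, so Cohort B response counts might still appear. In a section that analyses by subtype with A and B combined, cohort most naturally means subtype. Even on the kinder reading, no Cohort B-only ORR with an interval is named.

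A reader might infer three stronger things, and the documents do not support them:

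- **That the error rate is now 12% to 25%.** Such figures hold only conditional on assumed favourable Cohort A outcomes. For a pooled analysis fixed in advance, alpha is at most 10%.
- **That pooling was chosen because of the responses.** Nothing shows what was known when either text was written, or that it influenced the choice. With one dose explored, there was also little selection for Cohort A responses to drive.
- **That all five cohorts are affected.** SAP 2.4 says that Amendment 04 added PMBL and MGZL to the expansion phase, so they probably receive no Cohort A subjects. This is an inference; the documents do not state it.

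**Conclusion.** The conflict is real and should be corrected, but it is one of analysis set and traceability, with a modest numerical effect. The SAP keeps the protocol's additional analysis and drops the one that was sized, so SAP 5.1 and Protocol 8.1 no longer describe the primary ORR analysis. For the subtypes likely to be affected (DLBCL, PTCL, CTCL), with 1 to 6 added subjects, the threshold moves by up to four responders and power by between about −4 and +18 points (CTCL, m = 4: 18/24 gives 81.1% against 63.0%). The unconditional false-positive rate is not inflated. Choosing the set after seeing Cohort A would take it to 11.6% at worst with up to six subjects in a subtype; the documents do not show that this happened. All pooled figures rest on an assumed Cohort A mix and on reading the 80% interval against the null rates.

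**What to change.** In SAP 7.1 and 7.5.1, name ORR in Cohort B only, by subtype (B1 to B5), as the primary efficacy analysis, and report same-dose pooled A+B ORR as supportive. Keep pooling for the safety analyses. This restores the protocol's plan, needs no change in sample size, and leaves SAP 5.1 correct as it stands on this point. It also keeps subjects whose efficacy data were to inform the regimen out of the primary estimate.

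The cost is one extra table per subtype and a slightly smaller N, hence slightly wider intervals, in the primary estimate. If the sponsor prefers the pooled set as primary, the SAP should say that this departs from the protocol, justify it, and restate N, threshold and power by subtype.

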7.2 Study Conduct

7.2.1 Accrual

The accrual pattern will be summarized per country, investigational site and per month for all enrolled subjects. First dosing date, country, investigational site will be presented in a by subject listing of accrual.

7.2.2 Relevant Protocol Deviations

The relevant Protocol Deviations will be summarized for all treated subjects. A subject listing will also be produced. Relevant deviation implies a potential major impact on the interpretability of the main results of the study. Criteria for relevant deviations are listed below:

At entrance:

- Wrong diagnosis based on Exclusion/inclusion
- Do not have Measurable disease at baseline (not appliacable to CTCL)

On-study:

Use of the following prohibited medications during the study (unless utilized to treat a drug related adverse event):

• Any concurrent anti-neoplastic therapy (ie, chemotherapy, hormonal therapy, immunotherapy, extensive, non-palliative radiation therapy, or standard or investigational agents)

7.3 Study Population

7.3.1 Subject Disposition

The total number of subjects enrolled (treated or not treated) will be presented along with the reason for not being treated.

Number of subjects who discontinued study treatment along with corresponding reason will be tabulated.

A subject listing for all treated subjects will be provided showing the subject's first and last dosing date, off study date and reason for going off-study. A subject listing for subjects not treated will also be provided, showing the subject's race, gender, age, consent date and reason for not being treated.

7.3.2 Demographics and Other Baseline Characteristics

The following demographic and baseline characteristics of patient will be summarized. Listings will also be provided.

Baseline demographics:

- Age (descriptive statistics)
- Age category (< 65, ≥ 65 to <75, ≥ 75 to <85, ≥ 85)
- Gender, race, ethnicity

Baseline physical measurements

• ECOG, height, and weight

Other baseline characteristics:

- smoking status
- region (US/Canada, Europa and rest of the world)
- initial disease diagnosis
 - DLCL: DLCL or transformed lyphoma,
 - CTCL: Mycosis Fungoides (MF), Sezary Syndrome (SS)
 - PTCL: Angioimmunoblastic T Cell Lymphoma, Peripheral T Cell Lymphoma-NOS, Peripheral T Cell Lymphoma-Other
- stage of disease at initial diagnosis
- Disease status at study entry(relapsed, refractory or relapsed and refractory).
- Some disease characteristics will be reported depending on the NHL subtype:

DLBCL:

- international prognostic index (IPI) score at diagnosis,
- cell type involved at diagnosis and study entry.

CTCL:

• disease diagnosis at study entry: Mycosis Fungoides (MF), Sezary Syndrome (SS), other.

PTCL: no specific characteristics

PMBL: no specific characteristics

MGZL: no specific characteristics

- Time from Initial Disease Diagnosis to (< 1 year, 1 < 2 year, 2 < 3 year, 3 < 4 year, 4 < 5 year, ≥ 5 year)
- Lymphoma PET scan (yes/no), Lugano classification 5 point scale Lesion sites, Max SUV

- All lesions (Investigator Tumor Assessments at Baseline): sites of diseases, number of disease sites per subject
- Target Lesions (Investigator Tumor Assessments at Baseline): Presence of target lesions, site of target lesion, sum of product diameters of target lesions.
- Lymphoma involvement in bone marrow at baseline (Yes/No/Not Available)
- baseline efficacy assessement for CTCL: % BSA involvement, blood involved by peripheral blood cytometry, lymph node involved and tumor involved

7.3.3 Medical History

General medical history will be listed by subject and pretreatment events will be tabulated.

